Form FHS015: Research Protocol – Section C

Table of contents

- 1. Purpose of the study**
- 2. Background**
- 3. Methodology Pilot Study**
 - 3.1. Study design
 - 3.2. Characteristics of the study population
 - 3.3. Recruitment and enrolment
 - 3.4. Research procedures and data collection methods
 - 3.5. Data safety and monitoring
 - 3.6. Data analysis
- 4. Methodology RCT**
 - 4.1. Study design
 - 4.2. Characteristics of the study population
 - 4.3. Recruitment and enrolment
 - 4.4. Research procedures and data collection methods
 - 4.5. Data safety and monitoring
 - 4.6. Data analysis
- 5. Description of risks and benefits**
- 6. Informed consent process**
- 7. Privacy and confidentiality**
- 8. Reimbursement for participation**
- 9. Emergency care and insurance for research-related injuries**
- 10. What happens at the end of a study?**
- 11. References**
- 12. Appendices**

1. Purpose of the Study

This research project aims to increase access and uptake of contraception after abortion through the systematic development and testing of a new telemedicine service for contraceptive counselling (TECC). We will perform a pilot study in South Africa, and multicenter randomized controlled trial in South Africa and Kenya with the following specific aims:

1. To design and test a user-friendly online service for contraceptive counseling informed by systematic research into the preference and experience of women in our study setting.
2. To compare uptake of long-acting reversible contraception (LARC) after TECC and in-person contraceptive counseling.
3. To compare rates of choice, uptake, and continuation of LARC or any contraceptive, satisfaction, preference for counseling, recurrent unintended pregnancy, and recurrent abortion after TECC and in-person contraceptive counseling.

2. Background

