4.4. Research procedures and data collection methods RCT

4.4.1. Research procedures and data collection methods RCT – all participants

On the day of recruitment, a baseline survey will record participant demographic variables, socio-economic status, reproductive history, prior and current use of contraception, and frequency of use of the internet. Follow up surveys will be conducted 12 weeks, 6 months, and 12 months. Baseline and follow up surveys will be recorded either by women receiving a link to RedCap and filling out the questionnaires on their phones, or through a telephonic interview with the research assistant, depending on participant preference. At baseline, data for accessing the baseline survey on RedCap and using the TECC service will be provided to participants from the study staff by means of data hotspot/WIFI provided from study staff devices. The reimbursement amount will assist participants to cover costs for data required for the follow up survey and any contact with the TECC service after baseline. The participants also have the choice to participate in follow up surveys by phone interview with study staff. The baseline survey is expected to take about 10-15 minutes. The follow up survey at 12 weeks is expected to take about 20-25 minutes and follow up surveys at 6 months and 12 months are expected to take about 5-10 minutes. The questionnaires will capture primary and secondary outcomes as described below.

Outcomes

Primary outcome at 12 weeks

Uptake of LARC, defined as uptake of an IUD or a subdermal implant for contraception, within 12 weeks

Secondary outcomes at 12 weeks

1. choice of LARC

2. uptake of any contraception
3. choice or uptake of new method with regards to previous use
4. satisfaction with TECC service (using a multi-question validated scale)
5. Rated use of service for decision making (using a multi-question validated scale)
6. Degree of agency in decision making (using a multi-question validated scale)
7. preference for counselling

Secondary outcomes at 6 months

1. continued use of LARC
2. continued use of any contraception
3. recurrent unintended pregnancy
4. recurrent abortion

Secondary outcomes at 12 months

1. continued use of LARC
2. continued use of any contraception
3. recurrent unintended pregnancy
4. recurrent abortion
5. Change of method at any timepoint up to 12 months
6. Reason for change of method

Subsidiary outcomes

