4.6. Data analysis RCT

Continuous data will be presented as median (interquartile range) and dichotomous data as absolute (n) and relative (%) frequencies. Baseline data will be compared group-wise to ascertain successful randomization. Outcome data will be compared group-wise using Chi-square test according to intention to treat (ITT) among all randomized women according to allocation, and per-protocol (PP) according to the intervention women actually received. The risk ratio between groups of our main outcome and 95% confidence interval will be calculated using the STATA csi command.

Based on a previous RCT in the same setting we expect the baseline rate for our main outcome, uptake of LARC after abortion, to be 12%. We hypothesize that the intervention group using TECC will double their uptake of LARC. We also wish to be able to analyze our two study settings independently of each other. To show a doubling of uptake in a study group (effect size or odds ratio 2.0) corresponding to an absolute increase of 12%, with 95% confidence and 90% power we will need to analyze 212 women in each arm. This 95% confidence interval for that risk difference would in that case have a lower margin of 5% increase (corresponding to an OR of 1.5), which in a context of low use is considered clinically significant, i.e., the effect size of the intervention that we consider of clinical importance starts at 5%.

Based on previous studies we estimate that our loss to follow up will be up to 20% at 12 months bringing our sample to 510 women. Accounting for the statistical independency of the South African and Kenyan cohorts we double the sample for a total sample size of 1020 women of which 510 will be recruited in each country. This would give us 80% power and 95% confidence to determine a 12% difference in uptake of LARC in the intervention and control group at 12 weeks.

5. Description of Risks and Benefits

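### Section 4.6 describes the primary test among all randomised women but sizes the trial for a separate test in each country, and does not say which result answers aim 2

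*Protocol*

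**What the plan says.** The primary outcome (Protocol, section 4.4.1) is "Uptake of LARC, defined as uptake of an IUD or a subdermal implant for contraception, within 12 weeks". Aim 2 (section 1) is "To compare uptake of long-acting reversible contraception (LARC) after TECC and in-person contraceptive counseling"; it names no country.

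Section 4.6 then describes two units of analysis:

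- **All women.** Outcomes are compared by a "Chi-square test according to intention to treat (ITT) among all randomized women according to allocation", and one risk ratio with a 95% confidence interval is to be calculated for the main outcome with Stata's csi command.
- **Each country.** The section adds "We also wish to be able to analyze our two study settings independently of each other". It derives 212 women per arm (12% versus 24%, 95% confidence, 90% power), raises this to 510 women for loss to follow-up, and reaches 1020 with the words "Accounting for the statistical independency of the South African and Kenyan cohorts we double the sample".

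The section closes with a figure of 80% power for a 12-point difference at 12 weeks, without saying whether it refers to one country or to the total.

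**The concern.** The test sentence points to one comparison of 1020 women, while the sample size serves two comparisons of 510. Half of recruitment exists to make the country analyses possible, so they are not incidental. The section gives no rule for which result decides: the total, either country, or both.

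Two things are at stake. First, if any significant result may be presented as the answer to aim 2, the error rate is higher than the 95% confidence suggests. In a trial that section 4.3 says cannot be blinded, the deciding analysis could also be chosen after the results are known. Second, two separate country verdicts can disagree by chance when the effect is the same in both. Recruitment and control care differ by country (sections 4.3 and 4.4.3), so a split result would easily be explained as a real difference, which separate p-values cannot show. Section 10 intends the findings to inform guidelines in both countries.

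**Working it through.** **Inputs from section 4.6.** Control rate 12%, TECC rate 24%, 212 analysed per arm, 90% power, loss of up to 20%, 510 per country. Allocation is 1:1 (section 4.3). Sidedness is not stated; 95% confidence is read as two-sided alpha 0.05.

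**Reproducing the plan's figure.** With unpooled variance, n = (1.960 + 1.282)² × (0.12×0.88 + 0.24×0.76) / 0.12² = 10.51 × 0.288 / 0.0144 ≈ 211 per arm. With pooled variance under the null the result is 214. The stated 212 therefore reproduces as a two-sided test in one country; a one-sided test would need 174. The 510 reproduces as 2 × 212 × 1.2 = 509, rounded up. Taking 20% off 510 leaves 408, or 204 per arm; with no loss there are 255 per arm.

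**Error rate if TECC has no effect, each test at two-sided 0.05**

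- Two country tests, either of which may carry the claim: 1 − 0.95² = 9.75%. In favour of TECC only: 1 − 0.975² = 4.9%.
- Two country tests plus the pooled test: the pooled statistic is about (z₁ + z₂)/√2, with correlation 0.71 to each country statistic. Simulation (4 million draws) gives 11.5% two-sided and 5.8% in favour of TECC. Treating the three tests as independent would give 14.3%, which is too high because they overlap.
- Binomial simulation at 204 per arm agrees: 11.4% and 5.7%.

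**Disagreement between countries when the true effect is 12% versus 24% in both.** With power p in each country, exactly one test is significant with probability 2p(1 − p), and both with probability p².

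| Basis | p | Exactly one | Both |
|---|---|---|---|
| 255 per arm, no loss | 94.4% | 10.6% | 89.1% |
| Stated 90% power | 90.0% | 18.0% | 81.0% |
| 212 per arm | 89.8% | 18.3% | 80.7% |
| 204 per arm, 20% loss | 88.7% | 20.1% | 78.6% |
| Stated 80% power, if per country | 80.0% | 32.0% | 64.0% |

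Binomial simulation gives 19.6% for exactly one at 204 per arm and 10.1% at 255. At 12% versus 17%, the 5-point difference from which section 4.6 counts an effect as clinically important, the simulated figure at 204 per arm is 42%.

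**Which analysis the power statements describe.** The 90% fits one country with 212 per arm. The 80% fits neither unit: power is 88.7% per country at 204 per arm and 99.4% for both countries together at 408 per arm.

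**The case against.** A reader might infer that the protocol plans three tests and allows success on any of them, so that its type I error is simply not 5%. The text does not go that far. The words "among all randomized women according to allocation" also define intention to treat, in contrast to the per-protocol analysis, and no sentence says that the countries are pooled. The wish to analyse the settings independently states no success rule. Two coherent readings keep each claim at 5%: an overall test with country results as additional, or two country trials under one protocol. The error rates above are therefore conditional on an unstated rule.

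A flat figure of one in five for conflicting verdicts is also too strong. It needs the whole 20% loss, stated for 12 months, to have occurred by the 12-week outcome. Section 4.4.1 further plans to retrieve clinical records for women who cannot be reached. Moreover, any two studies with about 90% power will sometimes disagree; that becomes an error only if the disagreement is read as a country difference, and no passage says it will be.

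Testing rules are often left to the statistical analysis plan, which is not at hand, so the lack of a multiplicity rule is not itself a finding. The differences in recruitment, method distribution (section 4.4.2) and control care are also good reasons to want country results.

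What remains is a matter of the protocol's own text: section 4.6 sizes one analysis, describes another, does not name the deciding one, and gives two power figures that it does not reconcile.

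**Conclusion.** The point holds in this form. Section 4.6 leaves open whether the comparison over all women or the separate country tests answer aim 2. If any significant result may carry the claim, the error is 11.5% two-sided, or 5.8% in favour of TECC against a nominal 2.5%. With only the two country tests it is 9.75% two-sided. If one analysis is named in advance, that analysis keeps its 5%.

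Under an equal effect of 12% versus 24%, chance disagreement between the country tests lies between about 11% (no loss) and 20% (204 per arm), and is 32% if the 80% power figure is meant per country. These figures assume two-sided tests at 0.05, independent country samples, the planned rates and equal effects in both countries. The documents do not show that a three-way success rule is intended, nor that a country difference will be claimed from separate p-values.

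**What to change.** In section 4.6, name as the one confirmatory analysis the ITT comparison of LARC uptake over both countries, stratified by country: a Mantel-Haenszel test and risk ratio in place of the unstratified csi table. Report each country's risk ratio and risk difference with 95% confidence intervals, and the country-by-arm interaction, as supporting results. State that no country difference will be inferred from separate p-values. Say which analysis the 90% and 80% power figures describe and correct them: about 89% per country at 204 per arm, over 99% for both countries together.

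The change is to the text and needs no extra women. It has a real cost, however: a country result that is significant on its own no longer counts as confirmatory, and the doubling to 1020 then serves the precision of the country estimates rather than the confirmatory test.

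If the sponsor prefers a confirmatory claim per country, the protocol must say so in advance. Whether to adjust is then the sponsor's choice. With Holm's procedure, power per country would be at least about 82% at 204 per arm (the power at alpha 0.025); 90% at alpha 0.025 needs 253 analysed per arm.

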4.2. Characteristics of the study population RCT

Women in South Africa (n=510) and Kenya (n=510) seeking abortion at one of two community health clinics (CHCs), Mitchell's Plain CHC and Michael Mapongwana CHC in South Africa, and two CHCs in Kilifi and Mombasa (Kenya). The study population represents a low-income demographic but is not considered to include vulnerable populations.

Inclusion criteria:

Women seeking abortion either medical or surgical, ≤ 13 gestational weeks (GW), ≥ 18 years of age, able to communicate and understand spoken and written English, with private access to a smart phone, and willing to participate in the study.

Exclusion criteria:

No smartphone, not willing to participate in follow up, not fulfilling language criteria

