4.3. Recruitment, enrolment, and randomization RCT

Women will be informed about the study either at the abortion clinic (South Africa) or by phone through the collaborating abortion care hotline Reproductive Health Network Kenya (RHNK). All women in the South African arm of the study will be informed about the study while waiting to be seen for a consultation at the abortion clinics on a recruitment day. Interested women will be screened for eligibility. Eligible women will be recruited to the study after going through a private informed consent procedure with study staff.

Participants will be randomly allocated 1:1 to either TECC or in-person contraceptive counseling. The randomization sequence will be computer-generated 1:1 in permuted blocks of varying sizes by a researcher not involved in data collection and imported into the electronic research data capture tool RedCap. A research assistant will perform the randomization, in the presence of the participant on the same day as the intervention, by clicking on a link in the RedCap system which generated the next sequential number according to central allocation. Blinding of either the research assistant or participant to group allocation will not be possible.

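### Enrolling 510 women per country protects the required 212 analysed per arm only up to 16.9% loss, not the stated 20%; at 20% loss 204 per arm would remain

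*Protocol*

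**What the plan says.** All the sample size figures are in Protocol section 4.6.

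- Control rate: "we expect the baseline rate for our main outcome, uptake of LARC after abortion, to be 12" per cent.
- Target effect: "To show a doubling of uptake in a study group (effect size or odds ratio 2.0) corresponding to an absolute increase of 12" percentage points, so 24% in the TECC arm.
- Number to be analysed: "with 95% confidence and 90% power we will need to analyze 212 women in each arm".
- Loss allowance: "our loss to follow up will be up to 20% at 12 months bringing our sample to 510 women".
- Total: "we double the sample for a total sample size of 1020 women of which 510 will be recruited in each country". The reason given is that each country is to be analysable on its own, and section 4.2 repeats 510 for each country.
- Allocation (section 4.3): "Participants will be randomly allocated 1:1 to either TECC or in-person contraceptive counseling", so 255 per arm in each country.

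The last sentence of section 4.6 attaches 80% power, for the same 12-point difference at 12 weeks, to the final sample. The protocol does not write out how it got from 212 per arm to 510.

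**The concern.** The 212 is worded as a number to be analysed, that is, after losses. The 510 is presented as that number enlarged to absorb a loss of up to 20%. Loss is a share of the women enrolled, so the enrolled number times 0.8 should give back 424. It gives 408.

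Anyone using the section to judge retention would believe there is a 20% margin before the analysed number falls below its target, when the margin is 16.9%. Because the countries are meant to stand alone, the same gap applies in each of them.

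**Working it through.** **Inputs (section 4.6 unless noted).** Control 12%, intervention 24%, 212 analysed per arm, loss up to 20%, 510 enrolled per country, 1:1 allocation (section 4.3). Two-sided 5% is an assumption, read from the reference to 95% confidence. Loss is taken as equal in the two arms.

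**1. Reproduce 212.** With p1 = 0.12 and p2 = 0.24, the mean is 0.18 and the difference 0.12.

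- Unpooled variance: n = (1.960 + 1.282)² × (0.12 × 0.88 + 0.24 × 0.76) / 0.12² = 10.51 × 0.288 / 0.0144 ≈ 210.2, so 211 per arm.
- Pooled null variance: n = (1.960 × √(2 × 0.18 × 0.82) + 1.282 × √0.288)² / 0.12² ≈ 213.3, so 214 per arm.

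The stated 212 lies between them, so 90% power for 12% versus 24% is confirmed as its basis.

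**2. Reproduce 510.**

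- Multiplying by 1.2: 424 × 1.2 = 508.8; or per arm 212 × 1.2 = 254.4, rounded up to 255, and 2 × 255 = 510. This matches.
- Dividing by 1 − 0.20: 424 / 0.8 = 530 per country (265 per arm), 1060 in total. This does not match 510 and 1020.

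That the allowance was a multiplication by 1.2 is therefore an inference from the result.

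**3. What 510 delivers.** This step does not depend on how 510 was obtained.

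- At 20% loss: 510 × 0.8 = 408, or 204 per arm; 212 − 204 = 8 short (3.8%).
- Loss at which 424 are still kept: 1 − 424/510 = 86/510 = 16.9%.

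**4. Power per country.** Pooled z-test: power = Φ((0.12 × √n − 1.960 × √0.2952) / √0.288).

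- n = 212: (1.747 − 1.065) / 0.537 = 1.271, power 89.8%.
- n = 204: (1.714 − 1.065) / 0.537 = 1.209, power 88.7%.

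| Analysed per arm | Pooled | Unpooled |
|---|---|---|
| 204 (20% loss) | 88.7% | 89.1% |
| 212 (16.9% loss) | 89.8% | 90.2% |

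With no loss (255 per arm) the pooled figure is 94.4%.

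**5. The closing 80% figure.** For 12% versus 24%, 80% power needs 157 (unpooled) or 160 (pooled) per arm. Even 204 per arm is well above that, so the 80% follows neither from 212 nor from 204 per arm.

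**The case against.** The strongest reply is that the 20% and the 212 belong to different time points. The 212 is sized for LARC uptake by week 12 (section 4.4.1). The 20% is an upper limit for follow-up at 12 months, and the protocol gives no 12-week loss rate. Section 4.4.1 also provides that, for women who cannot be reached, contraceptive uptake will be looked up in clinical records in both countries. Section 4.6 places all randomised women in the intention-to-treat comparison. Loss for the primary outcome may well be below 16.9%, and then 212 per arm are kept.

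This stands, and it limits the point. A reader might infer that the trial will have only 204 women per arm, that it is underpowered, or that it must enrol 530 per country. The documents do not support any of these: nothing in them says that loss at 12 weeks will exceed 16.9%. Nor do they say how complete the records are, so they do not show that 212 will be met either.

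The size of the effect is also a fair objection. The choice between the two standard formulas already moves the target by 3 women per arm (211 or 214), against a worst-case gap of 8.

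What the reply does not remove is the mismatch on the page. The plan chose 20% as the loss to cover and 212 as the number to keep, and 510 does not do both.

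**Conclusion.** The point holds as a minor arithmetic inconsistency in section 4.6. If 20% of women lacked the 12-week outcome, 510 per country would leave 204 analysed per arm, 8 below the stated requirement, and power per country would be about 1.1 points lower (88.7% against 89.8% pooled; 89.1% against 90.2% unpooled). This is a worst case, and it rests on a two-sided 5% test, equal loss in the arms and no recovery of outcomes from records.

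It would be wrong to say that the protocol's power claim is simply overstated by a point. That is true only against the 90% used to derive 212. Against the 80% in the closing sentence, 204 per arm is more than enough. No analysis or design feature changes.

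**What to change.** No extra enrolment is needed. Restate the loss sentence in section 4.6 along these lines: 510 women per country leave 212 analysed per arm if loss for the 12-week outcome is at most 16.9%; at 20% loss, 204 per arm remain, giving about 89% power for 12% versus 24% in each country (two-sided 5%).

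In the same edit, reconcile the closing 80% power sentence with the 90% behind 212. Otherwise the section would carry three power figures (90%, about 89% and 80%) for the same comparison. Enrolling 530 per country (1060 in total) is needed only if the sponsor wants 212 per arm guaranteed at a full 20% loss.

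The cost is a short edit to one section, with no change to recruitment or analysis.

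### Section 4.6 states 90% and then 80% power for the same 12-point difference without explanation, and labels a risk ratio of 2.0 as an odds ratio

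*Protocol*

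**What the plan says.** All the relevant statements are in Protocol section 4.6.

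- Control-arm rate: the protocol expects "uptake of LARC after abortion, to be 12" percent, and hypothesises that the intervention doubles it.
- Effect label: the doubling is described as "effect size or odds ratio 2.0) corresponding to an absolute increase of 12" percent.
- First power statement: "with 95% confidence and 90% power we will need to analyze 212 women in each arm".
- Precision: the confidence interval for the risk difference is said to have a "lower margin of 5% increase (corresponding to an OR of 1.5").
- Allowance for loss: "our loss to follow up will be up to 20% at 12 months bringing our sample to 510 women". This is doubled to 1020 so that each country has 510.
- Reason for doubling: "We also wish to be able to analyze our two study settings independently of each other".
- Second power statement, closing the section: "This would give us 80% power and 95% confidence to determine a 12% difference in uptake of LARC" between the arms at 12 weeks.
- Planned effect measure: "The risk ratio between groups of our main outcome and 95% confidence interval will be calculated using the STATA csi command".

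**The concern.** The sample of 510 per country is built from a calculation at 90% power, yet the section ends by attributing 80% power to it. The section does not say whether the second figure is per country, for both countries together, or pooled.

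Power within each country is the stated ground for doubling the sample, so it is the figure most likely to be quoted from this section. A reader who takes the closing sentence at face value would report a per-country or pooled power that the design does not have.

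The effect label is a second, smaller problem. Doubling 12% to 24% is a risk ratio of 2.0, not an odds ratio of 2.0. The odds ratio of 1.5 in the next sentence is a true odds ratio. One label therefore covers two scales, while the planned effect measure is the risk ratio. Anyone rechecking the design from the label would start from the wrong alternative.

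**Working it through.** **Inputs.** From section 4.6: p1 = 0.12, p2 = 0.24, 95% confidence, 212 analysed per arm at 90% power, 510 randomised per country, loss up to 20%, chi-square test. From section 4.3: 1:1 allocation. Assumed: a two-sided 5% test, since the section does not state sidedness.

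**Formulas** (normal approximation, pooled variance under the null, n per arm)

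- Mean proportion: (0.12 + 0.24)/2 = 0.18
- A = √(2 × 0.18 × 0.82) = 0.5433
- B = √(0.12 × 0.88 + 0.24 × 0.76) = √0.288 = 0.5367
- n = (1.96·A + z_power·B)² / 0.12²
- power = Φ[(0.12·√n − 1.96·A)/B]

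**Step 1: the plan's own figure.** For 90% power, n = (1.0649 + 1.2816 × 0.5367)²/0.0144 = 213.3. Unpooled variance gives 210.1 and the arcsine method 209.8. The stated 212 lies among these, and its power is 89.8%. A one-sided test would need only 174, so 212 fits the two-sided assumption.

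**Step 2: power at the samples the section defines.**

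| Reading | Analysed per arm | Power |
|---|---|---|
| One country, 20% lost | 204 | 88.7% |
| One country, as calculated | 212 | 89.8% |
| One country, no loss | 255 | 94.4% |
| Pooled, 20% lost | 408 | 99.4% |
| Pooled, no loss | 510 | 99.9% |

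Exact enumeration gives 89.0%, 90.3%, 94.7% and 99.5% for the first four rows. A continuity correction lowers the per-country values to 86.0%, 87.4% and 92.9%. None is near 80%.

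**Step 3: what 80% would need.** n = (1.0649 + 0.8416 × 0.5367)²/0.0144 = 159.7, about 160 per arm. From 510 randomised, that is a loss of 1 − 2 × 159.7/510 = 37%, against a stated maximum of 20%.

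**Step 4: other routes to about 80%.**

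- Significance in both countries: 0.887² = 78.6% at 204 per arm and 0.898² = 80.7% at 212 per arm.
- A literal odds ratio of 2.0 (21.4% against 12%): 81.6% at 255 per arm with no loss. That is a difference of 9.4 points, not 12.

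**Step 5: why 20% loss leaves 204 rather than 212.** 510 matches 424 × 1.2 = 509. Dividing by the retained fraction gives 424/0.8 = 530. With 510 randomised, 212 per arm remain only if loss is at most 1 − 424/510 = 16.9%. The difference is about one point of power (89.8% to 88.7%), so it does not explain 80%.

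**Step 6: effect labels.**

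| Comparison | Risk ratio | Odds ratio | Section 4.6 says |
|---|---|---|---|
| 24% vs 12% | 2.00 | (0.24/0.76)/(0.12/0.88) = 2.32 | odds ratio 2.0 |
| 17% vs 12% | 1.42 | (0.17/0.83)/(0.12/0.88) = 1.50 | OR 1.5 |

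The 5-point lower limit reproduces: 0.12 − 1.96 × √(0.288/212) = 0.12 − 1.96 × 0.0369 = 0.048. Together with the 212 per arm, it confirms that 12% against 24% was the target. A literal odds ratio of 2.0 would have only 74.1% power at 212 per arm and would need 327 per arm for 90%.

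**The case against.** The strongest defence is that 80% means success in both countries. The sentence follows directly after the doubling for the two cohorts, and 0.90 × 0.90 = 0.81. This is a power the design does have. It stands as a possible reading, so the 80% is wrong only as a per-country or pooled figure. However, the section never requires both countries to succeed. It speaks of analysing them independently, and the closing sentence refers simply to a difference between the arms. The reader cannot tell that joint power is meant.

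A second objection is that the 20% loss is stated for 12 months, while the primary outcome is at 12 weeks and section 4.4.1 provides for retrieving missing uptake data from clinical records. That is fair, and it makes 204 per arm a worst case. Smaller loss raises the per-country power and moves it further from 80%.

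A third is that nothing operative changes. Read per country, 80% errs on the cautious side. The target is fixed by the 12% baseline, the doubling and the 12-point increase, and the planned analysis correctly names the risk ratio. This also stands, and it is why the point is minor.

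**Conclusion.** The point holds and is minor. Section 4.6 gives two powers for one difference, and the second has no stated basis. For 12% against 24%, power per country is about 89% to 94% with between 20% and no loss, and above 99% pooled. The stated 80% is about 9 to 14 points below the per-country power. It is near only to the joint probability of success in both countries, 79% to 81% at 204 to 212 per arm, which the text does not invoke. The trial is not underpowered for a 12-point difference.

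The odds ratio of 2.0 is a risk ratio of 2.0 (odds ratio 2.32), next to a correctly labelled odds ratio of 1.5.

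These results rest on a two-sided 5% chi-square test without continuity correction, 1:1 allocation, and the protocol's own rates. With the correction, per-country power at these sample sizes is 86% to 93%, and the conclusion is the same.

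**What to change.** Keep 510 per country and reword section 4.6 in two places.

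1. Give one power with its basis in the closing sentence, for example: *With 510 women per country, power to detect 24% against 12% (two-sided 5%) in each country is about 90% if 212 per arm are analysed (loss up to about 17%) and about 89% if loss reaches 20% (204 per arm).* If 80% was meant as the probability of success in both countries, say so and give it as about 79% to 81% at 204 to 212 per arm.
2. Replace the odds ratio of 2.0 with *risk ratio 2.0 (odds ratio about 2.3)*, and give the 5-point margin on the same scale as *risk ratio about 1.4 (odds ratio 1.5)*. Both then match the planned risk-ratio analysis.

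The cost is two wording corrections. Sample size, visits, analyses and participants are unaffected.
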